the utility of the research study in its application as a screening diagnostic tool to predict the subsequent occurrence of delayed vasospasm in subjects with an acute aneurysmal subarachnoid hemorrhage.

Study Methods

Inclusion criteria:

A total of 30 subjects will be enrolled in this pilot feasibility study. The following patients will be targeted for enrollment:

1. Patients with aneurysmal subarachnoid hemorrhage presenting to our institution within 24 hours of symptom onset.
2. Adults, 18 years of age or older
3. Women of childbearing potential must not be pregnant (urine pregnancy test will be required as is already done as part of standard of care)

Exclusion criteria:

Whether subjects will be invited to participate in this research will be based on the patient's medical condition and will be at the discretion of the treating physician. The following patients will be excluded automatically:

1. Contraindication to acetazolamide (i.e. sulfonamide allergy, renal or liver failure)
2. Contraindication to contrast media (Allergy or abnormal serum Cr and/or GFR based on current UW guidelines for IV contrast see Appendix A)
3. Renal insufficiency, history of renal failure or renal transplant
4. Hunt and Hess grade 1 and 5 (See Appendix B, as Grade 1 have lower yield for vasospasm and Grade 5 are by definition critically ill and unstable patients)
5. Critically ill patients who are unstable and who cannot undergo scans within the proposed timeline i.e. within 24 hours of the onset of their symptoms.

Patient identification/Recruitment/Consent:

Patients targeted for enrollment will be those referred to the Department of Neurosurgery and Neuroendovascular Surgery at University of Wisconsin meeting the inclusion criteria. Eligible candidates will be identified by the neuroendovascular or neurosurgical attending physician and will be invited to participate by a clinical care team member. If patients lack capacity to provide informed consent on their own behalf, the care team will include the next of kin in the consenting process. Subarachnoid hemorrhage patients that present with a medically unstable condition will not be considered for this study.

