Overview of imaging protocol: Prior to catheter angiography, the diagnostic evaluations of subjects entered into this protocol will not vary from that used on others who are not eligible or who do not wish to participate in the study. Subjects entered into the study, will because of their participation, undergo only two additional DSA imaging acquisitions. These will be done in conjunction with their standard diagnostic DSA evaluation and consist of two CBCTPs, one before and one after administration of 1 g acetazolamide through a peripheral IV line. Each CBCTP will require administration of 75-100 mL iodinated contrast medium also through an IV line. Neither of these imaging studies will be used for clinical decision making, but would be processed and evaluated at later date for a formal analysis of the results. Following completion of diagnostic imaging subjects will receive the usual standard of care for treatment of their ruptured aneurysm i.e. endovascular embolization or open surgical clipping.

Details of experimental imaging: An initial CBCTP acquisition will be done in conjunction with injection of iodinated contrast medium through a peripheral IV (75-100 mL iopamidol, Isovue 370; Bracco Diagnostics, Princeton, NJ). An IV is placed for normal standard-of-care for this disease process. After this 1 g of acetazolamide will be given through the IV line. Following a 20-minute delay a second CBCTP acquisition will be completed again in conjunction with injection of iodinated contrast medium at a dose identical to that used for the first CBCTP acquisition. Each of the CBCTP acquisitions take less than 2 minutes so, except for the 20-minute period following administration of the acetazolamide there will be no delay in the subjects' diagnosis or treatment.

Contrast: C-arm CBCTP will be performed with intravenous injection of contrast dye (iopamidol, Isovue 370; Bracco Diagnostics, Princeton, NJ) at a rate of 4 mL/s and a maximum dose range of 75-100 mL. The contrast bolus may be followed by a 50-mL saline push at a rate of 4 mL/s. The delay will be calculated from the conventional CTA/CTP that was performed prior. The contrast administered during the conventional CTA head and neck with perfusion performed prior will be 120 mL. Therefore, the maximum amount of IV contrast media that would be administered

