within a 24-hour period for this study is 320 mL. Contrast media administration is an important consideration as a cause of iatrogenic acute kidney injury, but it should be emphasized that the large majority of these cases are minor. Under our protocol pre- and post-procedure serum creatinine levels will be monitored closely and patients will receive adequate hydration. Iopamidol is excreted mainly through the kidneys and in the absence of renal dysfunction 35-50% of the contrast media is excreted within 60 minutes and 80-90% within 8 hours. There will be at least a 1 hour period between contrast loading from the conventional CTA/CTP and the study C-arm CBCT scans.

SMART RECON: This software utilizes the images acquired during rotational angiography to create an angiographic CT. The volume set is reconstructed on the syngo MultiModality Workplace and available for assessment in less than 1 minute in the interventional suite.

Data Acquisition: Perfusion maps from the standard multi-row CTP will be evaluated with the Siemens CTP software after the procedure. Perfusion maps from the C-arm CBCT will be evaluated at an independent work station with SMART RECON. Matching regions of interest (ROI's) will be placed in each hemisphere in mirror image positions. The ROI's identified on each patient's standard CTP will be compared to ones selected in the post-processing phase.

Acetazolamide injection: 1 g intravenous acetazolamide will be administered by peripheral IV. Blood pressure, respiratory rate, heart rate and pulse oximetry will be monitored before, during, and after this injection by the administering nurse. The wait period after drug administration will be standardized to 20 minutes prior to obtaining the follow up perfusion study.

Drug Information:

Drug formulation: Solution Reconstituted, Injection

Source: Drug is on UWHC formulary and would be available through the inpatient pharmacy
Storage and stability: Store intact vials at 20-25 C (68-77 F). Store reconstituted solutions for 3 days under refrigeration at 2-8 C (36-46 F), or 12 hours at room temperature (20-25 C or 68-77 F).

Preparation: For injection reconstitute with at least 5 mL sterile water to provide solution containing not more than 100 mg/mL.

Dosage/Administration: 1 gram, intravenous

For a complete listing of drug interactions, contraindications, and adverse reactions please see:
https://online.lexi.com/lco/action/doc/retrieve/docid/uofwisconsin_f/3680280

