Acetazolamide or the brand name Diamox is an FDA-approved medication with labeled indications including glaucoma, edema, altitude sickness, and epilepsy. Our protocol will utilize intravenous formulation only. Prior studies in the literature assessing cerebrovascular reserve used rapid 1 g intravenous injection over less than 1 minute¹¹. Doses of 500 mg were reported to be insufficient for adequate carbonic anhydrase inhibition¹². Acetazolamide is

contraindicated in patients with marked renal impairment, cirrhosis or liver disease, sulfonamide allergy, adrenocortical insufficiency, or hyperchloremic acidosis.

Risks:

This feasibility study presents minimal risks to participants. Subjects entering this study will not have the timing of their therapy, whether that be endovascular or open surgery, altered in any way that would differ from the standard of care offered at our institution. The potential risks from participating in this study include contrast and radiation exposure, side effects or adverse reactions to acetazolamide and the risk of breach of confidentiality.

Contrast exposure:

The main risks are allergic reaction and contrast-induced nephropathy (CIN). Prior to receiving the additional contrast media required by our study scan subjects will have already been given a prior dose of the same contrast medium for their standard of care conventional CTA. It will thus be clear to researchers whether the subjects are able to tolerate the agent. If any patient is experiencing any sign of contrast reaction at the conclusion of the clinical CTA, they will be withdrawn from this research study.

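### Does the 20-minute wait after acetazolamide contradict the promise of unaltered therapy timing in a way that calls for a change?

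*Combined protocol and SAP*

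**What the plan says.** Under Risks, the protocol states that subjects would "not have the timing of their therapy, whether that be endovascular or open surgery, altered in any way that would differ from the standard", meaning usual local care. The same section continues: "The potential risks from participating in this study include contrast and radiation exposure, side effects or adverse reactions to acetazolamide", and then adds breach of confidentiality. Waiting time is not on that list.

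Under Scan procedure, the overview says subjects "will because of their participation, undergo only two additional DSA imaging acquisitions", one before and one after acetazolamide. It adds: "These will be done in conjunction with their standard diagnostic DSA evaluation". On the order of events it says: "Following completion of diagnostic imaging subjects will receive the usual standard of care for treatment of their ruptured aneurysm". The details of experimental imaging state that "except for the 20-minute period following administration of the acetazolamide there will be no delay in the subjects' diagnosis or treatment". The paragraph on the acetazolamide injection says: "The wait period after drug administration will be standardized to 20 minutes".

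On renal eligibility, exclusion 2 covers contraindication to contrast media, including "abnormal serum Cr and/or GFR based on current UW guidelines for IV contrast see Appendix A". Appendix A has rows for iohexol, iodixanol and no IV contrast. The study agent is iopamidol. Exclusion 3 separately removes patients with renal insufficiency, exclusion 1 names renal failure, and invitation is at the treating physician's discretion.

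On contrast volume, Contrast exposure says the research total is below a 250 mL per-study maximum. The Contrast paragraph under Scan procedure gives 320 mL as the most given in 24 hours.

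**The concern.** These patients have a ruptured aneurysm, and some will be enrolled through next of kin. Unaltered therapy timing is offered as a safety property directly after the claim that risks are minimal. If one section denies any change and another concedes a 20-minute exception, an ethics board gets two answers to one question. The wait exists only because of the research: the extra acquisitions come with participation, and treatment follows imaging. The omission from the risk list points the same way.

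The renal rule raises a different worry. A screener holding a creatinine in one of Appendix A's iodixanol bands finds no stated outcome in exclusion 2, and the agent to be injected is not in the table. Two screeners might decide differently. Lastly, a reader who sets the 250 mL remark beside the 320 mL total may think one of them is wrong.

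**Working it through.** No power, sample-size or error-rate figure bears on this point. The check is a comparison of passages with some addition.

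**Timing**

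1. Inputs: a 20-minute wait (Details of experimental imaging; Acetazolamide injection) and two acquisitions of less than 2 minutes each (Details of experimental imaging).
2. Research-only time in the suite: at least 20 minutes, and under 20 + 2 × 2 = 24 minutes, not counting injection or set-up. The protocol counts only the 20 minutes as an exception.
3. Subjects still to be enrolled at this amendment: 30 − 10 = 20 (Study Objective).
4. For scale only, 20 / (24 × 60) = 20 / 1440 = 1.4% of the 24-hour window from symptom onset. That window governs eligibility and scanning. It is not a time-to-treatment target, so the percentage says nothing about clinical importance.
5. Side by side, the Risks sentence concerns when therapy happens relative to local standard of care. The Scan procedure sentence concerns delay in diagnosis or treatment and sits inside a session shared with the standard angiogram. The wait may overlap routine imaging or follow it; neither section says which. The shift in therapy could therefore be anywhere from 0 to 20 minutes on account of the wait.
6. The Contrast paragraph also requires at least 1 hour between the conventional CT contrast and the study scans. Whether that adds waiting depends on when the angiogram would otherwise begin, which is not stated, so it is not counted.
7. Effect on the data: both places that specify the interval between drug and second scan give 20 minutes, the same for every subject. The paired comparison before and after acetazolamide is therefore defined consistently, whichever way the risk sentence is worded.

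**Renal criterion**

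| Status | Iodixanol band | No IV contrast row |
|---|---|---|
| Diabetic | creatinine 1.4–2.0; eGFR 45–30 | creatinine > 2.0; eGFR < 30 |
| Non-diabetic | creatinine 1.8–3.0; eGFR 30–15 | creatinine > 3.0; eGFR < 15 |

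Exclusion 2 is about contraindication to contrast, and the row it maps to most directly is the one that bars IV contrast with any agent. For the bands above that row, exclusions 1 and 3 and the treating physician's discretion still operate, though without a number. The documents do not allow an estimate of how many candidates fall there.

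**Contrast volume**

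- Research scans: 2 × 75 = 150 mL to 2 × 100 = 200 mL, both below 250 mL.
- 24-hour total with the 120 mL conventional CT: 120 + 150 = 270 mL to 120 + 200 = 320 mL. The upper figure reproduces the protocol's maximum.
- The 250 mL figure is a maximum for a given study. A 24-hour total across separate examinations is a different quantity, so the two statements do not conflict.

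**The case for a change.** The strongest case for acting is that an exception to a statement of no delay is, in plain English, a delay. The qualifier about standard of care does not obviously rescue the Risks sentence, because the wait is a research procedure that non-participants do not undergo. If overlap with the standard angiogram is the explanation, one sentence would have said so. With 20 subjects still to enrol, the text could be tidied in time to help most of the cohort.

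What stands is the mismatch in wording: one sentence carries an exception and the other does not, and the two passages have to be reconciled by the investigators. What does not stand is the step from there to a problem with the plan. The wait is disclosed in two paragraphs of the Scan procedure, so an ethics board reading the protocol sees it. The risk list is introduced as what the risks include, and need not be exhaustive. Consent pages are not available, so nothing can be inferred about what participants or surrogates were told.

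On the renal rule, it stands that iopamidol has no row in Appendix A and that the middle bands have no numerical outcome. That is missing detail rather than contradiction. The exclusion cites current institutional guidelines that may say more than the appendix reproduces, and a single-centre pilot with discretionary enrolment can settle such cases at the bedside. Nothing remains of the contrast-volume point.

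**Conclusion.** The sentences on timing disagree as written, by at most the 20-minute wait, and the documents do not show that therapy moves by that amount or that such a shift would matter clinically. This is a clerical mismatch in risk wording about a step that is specified consistently and disclosed. Bringing the two sentences into line is an editorial matter for the investigators and the ethics board. It alters neither what is done to subjects nor what the study can conclude: scans, sample size and analysis stay the same. The renal criterion leaves a gap that the other exclusions and clinical judgement are there to fill; where the limit lies is for the investigators and the ethics board. The contrast statements are both correct for what they describe.

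The conclusion rests on two assumptions: that the Scan procedure text governs what happens in the suite, and that screeners apply exclusions 1 to 3 together rather than exclusion 2 alone. No change to the plan is called for.

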As it pertains to CIN, the standard maximum dose for a given study is 250 mL and the total dose for subjects participating in our research scans will be less than this. In a study of 11,588 patients undergoing CT scans with or without administration of contrast medium, Bruce and colleagues at UW-Madison concluded: "We identified a high incidence of acute kidney injury among control subjects undergoing *unenhanced* CT. The incidence of creatinine elevation in this group was statistically similar to that in the iso-osmolar contrast medium group for all baseline creatinine values and all stages of chronic kidney disease. These findings suggest that the additional risk of acute kidney injury accompanying administration of contrast medium (contrast-induced nephrotoxicity) may be overstated and that much of the creatinine elevation in these patients is attributable to background fluctuation, underlying disease, or treatment.". In another study of 1,075 patients receiving routine CT angiography and CT perfusion, Josephson and colleagues 52 patients had a creatinine rise of $>$ or $=$ to 0.5 mg/dL. In 4 (0.37%) the administration of IV contrast medium possibly contributed to renal failure. They concluded that "The incidence of contrast nephropathy in neurovascular patients is low". Thus, both our experience and additional literature support our belief that this small amount of added contrast dose poses virtually no added risk to these subjects when used as described in this protocol^{21,22}. Additionally, in the 2017 American College of Radiology Manual on Contrast Media they report that there is not sufficient evidence to specifically endorse the decision to withhold a repeat contrast medium injection until more than 24 hours have passed nor to recommend a specific threshold of contrast medium volume beyond which additional contrast media should not be given within at 24-hour period.

Radiation exposure:

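### Does the assurance that subjects receive less than 250 mL of contrast contradict the protocol's own 320 mL total?

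*Combined protocol and SAP*

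**What the plan says.** Under Scan procedure, each of the two research perfusion scans uses 75-100 mL of IV iopamidol, the second at the same dose as the first. For the earlier clinical scan: "The contrast administered during the conventional CTA head and neck with perfusion performed prior will be 120 mL". The Contrast paragraph adds these and states that the maximum IV amount "within a 24-hour period for this study is 320 mL". It then says that "pre- and post-procedure serum creatinine levels will be monitored closely and patients will receive adequate hydration", and on timing: "There will be at least a 1 hour period between contrast loading" at the clinical scan and the research scans.

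Under Risks, Contrast exposure, the protocol says that "the standard maximum dose for a given study is 250 mL" and that "the total dose for subjects participating in our research scans will be less than this". It concludes that "this small amount of added contrast dose poses virtually no added risk to these subjects", and reports that the cited contrast manual finds too little evidence to endorse a 24-hour wait "nor to recommend a specific threshold of contrast medium volume beyond which additional contrast media should not be given" in that period.

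Exclusion 2 refers to Appendix A for renal limits. Appendix A has rows for iohexol, for iodixanol and for no IV contrast, and none for iopamidol. Exclusions 1 and 3 separately remove renal failure, renal insufficiency and renal transplant.

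**The concern.** A reader who takes the total dose as everything given in the 24 hours finds 320 mL in one section and an assurance of less than 250 mL in another. The Contrast paragraph invites this by attaching the word study to the cumulative figure, while the risk section attaches the same word to the 250 mL ceiling. The risk section prints no other contrast volume and calls the addition small without giving its size. If the assurance were false, one support for the low nephropathy risk statement would fail.

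The second worry is eligibility. Screeners are sent to a table that does not name the agent given, so the renal cut-off for that agent may seem undefined. The tolerance argument under Contrast exposure also assumes that the clinical CTA used the same medium, and the protocol does not name the CTA agent.

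**Working it through.** **Inputs.** Research injections: two, each 75-100 mL, equal doses (Scan procedure). Clinical CTA/CTP: 120 mL (Contrast paragraph). Reference figure: 250 mL (Contrast exposure).

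**1. The plan's own figure.** Maximum = 120 + 2 × 100 = 320 mL, which matches the printed value.

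**2. Two readings of the total, set against 250 mL.**

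| Reading | Low end | High end | Share of 250 mL |
|---|---|---|---|
| Research injections only | 2 × 75 = 150 mL | 2 × 100 = 200 mL | 60% to 80% |
| 24-hour IV sum | 120 + 150 = 270 mL | 120 + 200 = 320 mL | 108% to 128% |

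The first row is below 250 mL throughout. The second exceeds it by 270 − 250 = 20 mL to 320 − 250 = 70 mL. The 270 mL is derived and treats 75 mL as a firm floor. Scan procedure supports that in one place but elsewhere calls 75-100 mL a maximum range, so the low end is less certain than the high end.

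**3. Which reading the text supports.** Three cues point to the research injections alone:
- The assurance itself speaks of the research scans, and the conclusion speaks of added contrast.
- The preceding paragraph in Contrast exposure sets the additional contrast needed for the study scan apart from the clinical CTA dose already given.
- Scan procedure uses the word study for a single imaging examination, so a maximum for a given study is naturally a per-examination figure.

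One cue points the other way: the 320 mL is described as the 24-hour amount for this study. On balance the research-only reading is better supported, and under it the sentence is correct. Setting 250 mL against a 24-hour sum compares a per-study figure with something the protocol does not apply it to.

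**4. Size of the increment.** Relative to the clinical dose: 150/120 = 1.25 and 200/120 = 1.67. As a share of the 24-hour IV sum: 150/270 = 56% and 200/320 = 63%. These qualify the adjective small, but they follow from volumes the protocol prints.

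**5. Appendix A.** The rows for no IV contrast (diabetic: creatinine above 2.0 or eGFR below 30; non-diabetic: above 3.0 or below 15) name no agent, so they apply to iopamidol. The gap is in the middle bands: diabetic creatinine 1.4-2.0 or eGFR 45-30, and non-diabetic 1.8-3.0 or 30-15. There the table assigns iodixanol, and the protocol does not say whether such a patient is abnormal under exclusion 2. Exclusion 3 probably removes many of them, though it gives no number.

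**6. Agent match.** Contrast exposure states that the CTA used the same medium, and the Contrast paragraph discusses iopamidol excretion just before the interval between the two scans. Both are consistent with one agent. Nothing says the CTA agent is chosen from Appendix A; that would be an inference.

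**7. Effect on the analysis.** The planned comparison is CBF before against after acetazolamide, with equal contrast doses at both scans. Neither the cumulative volume nor the 250 mL figure enters it.

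**The case for a change.** The best case for a change is that a risk section should be readable on its own. This one offers 250 mL as its only volume, does not say what the total covers, and calls small an addition larger than the clinical dose. A few words would settle it at no cost. Likewise, a screener with a middle-band patient has no explicit answer from Appendix A.

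Much of this is fair. The term is undefined, and a cumulative reading is possible. If the sponsor did mean the cumulative total, the two sections would conflict and would have to be reconciled. The middle-band question is also real.

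But the 320 mL is not hidden: it stands immediately before the discussion of kidney injury, with creatinine monitoring, hydration and the minimum interval. Restating it under Risks would add no information. The 250 mL sentence is one support among several, beside two cited cohorts and the manual's position on volume thresholds. Enrolment is already at the treating physician's discretion, with two further renal exclusions.

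**Conclusion.** No change to the plan follows. The assurance holds for the research injections (150-200 mL against 250 mL), which is the better-supported reading. It would fail only if set against a 24-hour IV sum of 270-320 mL, to which the protocol does not apply the 250 mL figure. The agent point is narrower than it first appears: it concerns only how middle-band patients are classified under exclusion 2, and the documents give no count of such patients.

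This rests on the research-only reading, on 75 mL as the floor for the 270 mL figure, and on counting IV contrast only, since no volume is given for the catheter angiography. No unsafe dose or concealment is shown, and the endpoint and analysis are unaffected. Any limit, agent or renal rule is for the sponsor to settle; none is judged or proposed here.
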